5.3 Dose Modifications

5.3.1 Pembrolizumab Dose Modifications

Retreatment criteria for pembrolizumab and cisplatin are independent (retreatment criteria for cisplatin are specified in section 5.3.2 below). There are no dose reductions for pembrolizumab. If the subject meets retreatment criteria, the full dose of 200 mg will be administered. If subjects do not meet retreatment criteria, then the dose of pembrolizumab will be SKIPPED. The sole exception to this rule is the first dose of pembrolizumab following completion of chemoradiotherapy, on both Arms 1 and 2. Although scheduled for

Week 10 of protocol treatment, the first post-chemoradiotherapy dose of pembrolizumab may be DELAYED up to 3 weeks to allow for recovery from acute toxicities, in accordance with the treating investigator's judgment. In the case of such delay, the following three doses of pembrolizumab will then be scheduled every 3 weeks (+/- 3 days) from the first post-chemoradiotherapy dose.

Subjects should receive appropriate supportive care measures as deemed necessary by the treating investigator. Suggested supportive care measures for the management of adverse events with potential immunologic etiology are outlined in Table 4 below and in greater detail below. Where appropriate, these guidelines include the use of oral or intravenous treatment with corticosteroids as well as additional anti-inflammatory agents if symptoms do not improve with administration of corticosteroids. Note that several courses of steroid tapering may be necessary as symptoms may worsen when the steroid dose is decreased. For each disorder, attempts should be made to rule out other causes such as metastatic disease or bacterial or viral infection, which might require additional supportive care. The treatment guidelines are intended to be applied when the investigator determines the events to be related to pembrolizumab.

Note: if after the evaluation the event is determined not to be related to pembrolizumab, the investigator is instructed to follow the Events of Clinical Interest (ECI) reporting guidance but does not need to follow the treatment guidance (as outlined in the ECI guidance document). Please see section 12.4.2 for ECI reporting guidance.

It may be necessary to perform conditional procedures such as bronchoscopy, endoscopy, or skin photography as part of evaluation of the event. Suggested conditional procedures, as appropriate, can be found in the ECI guidance document.

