8.2 Evaluations during treatment

8.2.1 Arm 1 (Cisplatin-IMRT followed by sequential pembrolizumab)

ARM 1, WEEKS 1-7 (During

concurrent cisplatin-IMRT)

Weekly:

Note: The following assessments will be performed weekly and may be performed on the day of or the day prior to cisplatin administration.

- History and physical examination.
- Vital signs, including weight.
- Toxicity assessment with attribution.
- Update of concomitant medications.

- Complete blood count, including platelets and differential.
- Blood chemistries (may be obtained from whole blood or serum/plasma sample), including creatinine, electrolytes (K+, Na+, Cl-, CO₂), calcium, Mg++ and liver function tests [bilirubin, AST (SGOT), ALT (SGPT), and alkaline phosphatase, total protein, albumin].

Every 3 weeks (Week 3 and Week 6):

Note: The following assessments will be performed every 3 weeks during concurrent cisplatin-IMRT and may be performed on the day of or the day prior to cisplatin administration. It is recommended that research blood should be coupled to the standard of care blood draw, to minimize needle sticks to the patient.

- Thyroid function tests (TSH, FT4).

Once (Week 6):

- Anti-thyroglobulin antibody, thyroid peroxidase antibody, thyroid stimulating immunoglobulin, and ANA.

ARM 1, WEEKS 8-31 (During sequential

pembrolizumab treatment): Every 3 weeks (Week 9, 12, 15, 18, 21, 24, 25, 30):

Note: The following assessments will be performed every 3 weeks, and may be performed on the day of or the day prior to pembrolizumab administration.

- History and physical examination.
- Vital signs, including weight.
- Toxicity assessment with attribution, including irAE assessment.
- Update of concomitant medications.
- Complete blood count, including platelets and differential.
- Blood chemistries (may be obtained from whole blood or serum/plasma sample), including creatinine, electrolytes (K+, Na+, Cl-, CO₂), calcium, Mg⁺⁺ and liver function tests [bilirubin, AST (SGOT), ALT (SGPT), and alkaline phosphatase, total protein, albumin] .
- Thyroid function tests (TSH, FT4).

Twice (Week 18, Week 30; these will be performed at the 4th and 8th doses of pembrolizumab, respectively):

- Anti-thyroglobulin antibody, thyroid peroxidase antibody, thyroid stimulating immunoglobulin, and ANA.

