8.3 Post-treatment Evaluations

8.3.1 Response Assessment

8.3.1.1 RECIST 1.1. Response assessment by RECIST 1.1 is required; integrated PET/CT interpretation is strongly recommended where available.

Twelve to 14 weeks following completion of cisplatin-IMRT (week 20-22 of protocol treatment), patients on both treatment arms will undergo diagnostic contrasted CT scan of the neck and chest, to assess treatment response according to RECIST 1.1. In the case where MRI of the neck was required for baseline tumor measurements, MRI of the neck should be repeated for response assessment, with non-contrasted diagnostic CT of the chest. Note: where available, an integrated PET/CT with contrasted diagnostic CT scans of the neck and chest is strongly preferred for response assessment.

8.3.1.2 Evaluation by an otolaryngologist with endoscopy as indicated.

8.3.1.3 The patient will be evaluated by the otolaryngologist 12-14 weeks following completion of cisplatin-IMRT (during weeks 20-22). Endoscopy for oropharyngeal or unknown primary carcinoma will be performed for response assessment as clinically indicated, and is at the discretion of the surgeon. Endoscopy is required for hypopharyngeal and laryngeal carcinoma. The surgeon will evaluate the need for primary site biopsy and/or neck dissection.

8.3.2 End of Treatment Visit(s): Week 33 (+/- 2 weeks) for Arm 1; Week 24 (+/- 2 weeks) for Arm 2. Patients will undergo the following procedures at the end of treatment visit:

- History and physical examination and performance status.
- Assessment for resolution of toxicities, including irAE, with attribution.
- Thyroid function testing (TSH, T3, FT4).
- Complete blood count, including platelets and differential.
- Blood chemistries (may be obtained from whole blood or serum/plasma sample), including BUN, creatinine, electrolytes (K+, Na+, Cl-, CO2), calcium, Mg++ and liver function tests (bilirubin, AST (SGOT), ALT (SGPT), and alkaline phosphatase, total protein, albumin).
- Audiogram assessment as indicated.

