SLP consult ^j	x														x
Audiogram ^j	x														x
Cisplatin ^q		x	x	x	x	x	x	x	x						
Pembrolizumab		x			x			x		x	x	x	x	x	
IMRT		x	x	x	x	x	x	x	x						
Adverse event evaluation		x	x	x	x	x	x	x	x	x	x	x	x	x	x

a. Pre-treatment evaluations will be performed within 4 weeks prior to registration, unless otherwise specified.

b. Complete blood count with differential (CBCDs) should include WBC, ANC, PLT, Hb, Hct. CBCDs required for protocol therapy may be performed on the day of or the day prior to cisplatin/pembrolizumab administration.

- c. Blood chemistry should include Na, K, Cl, CO₂, BUN, Cr, Glucose, Ca and Magnesium and be either Serum or Whole blood based on institutional practices/policies.
- d. Liver function tests should include SGOT (AST), SGPT (ALT), total bilirubin, total protein, albumin, alkaline phosphatase.
- e. Thyroid function studies (TSH, FT4) are required at baseline, and at weeks 3, 6, 9, 12, 15, 18, 21, 24, 27, 30, and recommended at week 33 f/u (Arm 1); TSH, FT4 is required at baseline, and at weeks 3, 6, 9, 12, 15, 18, and 21 and recommended at week 24 f/u (Arm 2). TSH and FT4 are required at 6, 9, 12, 18, 24, 36, 48, and 60 month follow-up in both Arms.
- f. A diagnostic contrast CT of the neck and chest will be conducted for staging and tumor measurements at baseline, and 12-14 weeks after completing IMRT. If feasible at participating sites, an integrated PET/CT with diagnostic contrasted CT is recommended at both time points. Tumor measurements will be conducted in accordance with RECIST 1.1. Rare patients may require an MRI for tumor measurements, due to allergy to iodinated contrast despite premedication. In these patients, MRI of the neck should be performed at baseline and at first response assessment. During long term f/u, neck MRI should continue to be performed in the place of neck CT.
- g. Integrated PET/CT with diagnostic contrasted neck CT is strongly recommended at pre-study baseline and 12-14 weeks after completing IMRT. However, PET/CT is not required for study participation.
- h. CT of the neck (or MRI in those with iodinated contrast allergy) will be conducted at the following intervals post IMRT: 6 mos, 9 mos, 12 mos, 18 mos, 24 mos. More intensive imaging may be conducted per local practice.
- i. Chest CT (without contrast in those with iodinated contrast allergy) will be conducted at the following intervals post IMRT: 6 mos, 9 mos, 12 mos, 18 mos, 24 mos.

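### Pembrolizumab schedule entries are wrong as written: Arm 1 week 25 should be week 27, and Section 5.3.1 schedules three doses after a delay when seven (Arm 1) or four (Arm 2) remain

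*Combined protocol and SAP*

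**What the plan says.** Section 5 plans eight 200 mg doses per arm at 3-week intervals, with a tolerance of 3 days either way. It lets the week 9 dose slip by up to 3 weeks and then has every later dose follow at 3-week intervals, in both arms. Section 5.1.3 repeats the interval and Section 5.5 repeats the total of eight.

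Three places depart from this or sit awkwardly with it:

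- **Arm 1 weeks.** The pembrolizumab row of Table 2 runs 9, 12, 15, 18, 21, 24, 25, 30. Section 8.2.1 gives the same list: "Every 3 weeks (Week 9, 12, 15, 18, 21, 24, 25, 30". Its note reads: "The following assessments will be performed every 3 weeks, and may be performed on the day of or the day prior to pembrolizumab administration". In Appendix C, the Arm 1 calendar header has week 27, and so does footnote e on thyroid tests: "weeks 3, 6, 9, 12, 15, 18, 21, 24, 27, 30, and recommended at week 33 f/u (Arm 1".
- **Doses after a delay.** Section 5.3.1, in an exception that it applies to both arms, says: "In the case of such delay, the following three doses of pembrolizumab will then be scheduled every 3 weeks (+/- 3 days".
- **Week label.** The same paragraph of Section 5.3.1 places the dose at "Week 10 of protocol treatment, the first post-chemoradiotherapy dose of pembrolizumab may be DELAYED up to 3 weeks". Section 5, Tables 2 and 3, Sections 8.2.1 and 8.2.2 and Appendix C all use week 9.

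**The concern.** Table 2 is the dosing table, Section 8.2.1 ties its visits to the day of dosing or the day before, and Section 5.3.1 is where a site would look when a patient needs longer to recover from chemoradiotherapy. An error in any of these can reach a patient. Followed literally, Table 2 gives two 200 mg doses 7 days apart and then nothing for 5 weeks. A site working from Section 5.3.1 by itself has no timing for the doses after the third. What is at stake is avoidable protocol deviations and site queries about the experimental drug, in a trial whose primary objective is to evaluate two schedules of it.

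**Working it through.** **Inputs.** Eight doses per arm (Sections 5 and 5.5). Interval 21 ± 3 days, so 18 to 24 days (Sections 5, 5.1.2 and 5.1.3). Arm 1 starts at week 9. Arm 2 weeks from Table 3, which has no week 0.

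**The plan's own count reproduces.** Arm 1: 9 + 3i for i = 0 to 7 gives 9, 12, 15, 18, 21, 24, 27, 30, which is eight doses and matches Appendix C. Arm 2: -1, 3, 6, 9, 12, 15, 18, 21, which is eight doses with seven gaps of 21 days.

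**Arm 1 gaps.**

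| Source | Last four weeks listed | All seven gaps (days) |
|---|---|---|
| Table 2 and 8.2.1 | 21, 24, 25, 30 | 21, 21, 21, 21, 21, 7, 35 |
| Appendix C | 21, 24, 27, 30 | 21, 21, 21, 21, 21, 21, 21 |

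The 7-day gap is 18 - 7 = 11 days too short. The 35-day gap is 35 - 24 = 11 days too long.

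**Which week is intended.** Section 8.2.1 fixes two doses by number: "Twice (Week 18, Week 30; these will be performed at the 4th and 8th doses of pembrolizumab, respectively". From dose 4 to dose 8 there are four intervals over 30 - 18 = 12 weeks, or 12 / 4 = 3 weeks each. Doses 5, 6 and 7 therefore fall at weeks 21, 24 and 27. The end-of-treatment visits in Section 8.3.2 are set at "Week 33 (+/- 2 weeks) for Arm 1; Week 24 (+/- 2 weeks) for Arm 2". That is 33 - 30 = 3 weeks and 24 - 21 = 3 weeks after an undelayed eighth dose, the same spacing in both arms.

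**Doses remaining after the first post-chemoradiotherapy dose.**

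- Arm 1: it is dose 1, so 8 - 1 = 7 remain. Three are named in 5.3.1, and 7 - 3 = 4 are left without a schedule there.
- Arm 2: it is dose 4, so 8 - 4 = 4 remain (weeks 12, 15, 18, 21). Three are named, and 4 - 3 = 1 is left.

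The 15-week Arm 2 maintenance period in Section 5 agrees: 15 / 3 = 5 doses, one plus four.

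**Week label.** With a delay of up to 3 weeks, the latest start is 9 + 3 = week 12 by Section 5. If week 10 in 5.3.1 is read on the same calendar, it is 10 + 3 = week 13.

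**The case against.** The strongest reply is that no careful site would be misled. The Section 8.2.1 list is headed as 3-weekly, Table 2 sits beneath text that gives the interval and the number of doses, and weeks 24, 25 and 30 look like a slip. Section 8.2.1 is also an assessment list and not a dosing order. This stands as far as intent goes, and it keeps the point minor. It does not make the entries right. Week 25 is in the dosing table and again in running text, so it is not an artefact of reading the PDF.

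A reader might infer that Section 5.3.1 cuts the course short after a delay, to 1 + 3 = 4 doses in Arm 1 or 3 + 1 + 3 = 7 in Arm 2. The documents do not support that. The sentence sets timing for three doses. It contains no limiting word and no instruction to stop, and Section 5.5 keeps the total at eight. For the three doses that it names, it agrees with Section 5. For the rest it is silent, and Section 5 supplies the answer. Incomplete is the fair description.

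A reader might also take week 10 as plainly wrong for both arms. In Arm 2, counting from week -1 with no week 0, the column labelled 9 is the tenth week of treatment, so the label can be read as correct there. The documents do not say that this was meant, and it does not help Arm 1, which Section 5 places at week 9.

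Finally, a reader might want the plan to state that a skipped dose is never made up. Section 5.3.1 says: "If subjects do not meet retreatment criteria, then the dose of pembrolizumab will be SKIPPED". Whether a skipped dose may be added at the end is a separate treatment rule. It corrects neither inconsistency.

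**Conclusion.** The entries are wrong as written, and the severity is minor. Arm 1 week 25 produces two gaps, each 11 days outside the permitted window, where week 27 produces none. The Section 5.3.1 sentence leaves four planned Arm 1 doses and one planned Arm 2 dose without a schedule and matches neither arm. The week 10 label is a smaller inconsistency, clear for Arm 1 and arguable for Arm 2.

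This rests on taking Section 5 (eight doses, 3-weekly, all later doses moved together) and Appendix C as the intended schedule. Sections 5.1.3, 5.5 and 8.3.2 and the numbered doses in Section 8.2.1 all support that.

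A reader might infer that the statistical plan or the concurrent versus sequential contrast is compromised. It is not. The sample size, the confidence-interval acceptance criteria and the DLT stopping boundaries do not use these dose weeks, and the arms still differ in when pembrolizumab starts.

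**What to change.** - In Table 2 and Section 8.2.1, change Arm 1 week 25 to week 27.
- In Section 5.3.1, replace the reference to three doses with all subsequent planned doses, so that it agrees with Section 5.
- In Section 5.3.1, change week 10 to week 9.

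Ask the sponsor separately whether a skipped dose may be added at the end of the course. Do not settle that within this correction.

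The cost is a few word-level edits. No patients, procedures or statistical changes are needed.

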Table 4. Pembrolizumab Dose Modification Guidelines for Drug-Related Adverse Events

Toxicity	Hold Pembrolizumab For NCI CTCAE Grade	Timing for Restarting Treatment	Discontinue Pembrolizumab Permanently
Out-of-field Rash (skin rash outside of the radiation field)	3	Toxicity resolves to Grade 0-1 and the patient has tapered off of or did not require systemic corticosteroids. (Ongoing management with topical steroids is acceptable.)	Toxicity does not resolve within 12 weeks of last dose or inability to taper off of corticosteroids within 12 weeks.
In-field radiation dermatitis (skin rash within the radiation field) – Arm 2	4 ^a	Toxicity resolves to Grade 3 or less. NOTE: systemic and topical steroids should be avoided in the case of radiation dermatitis that is restricted to in-field.	Toxicity does not resolve to Grade 3 or better within 6 weeks of completing IMRT
Diarrhea/Colitis	2-3	Toxicity resolves to Grade 0-1 and the patient has successfully tapered off of corticosteroids.	Toxicity does not resolve within 12 weeks of last dose or inability to taper off of corticosteroids within 12 weeks.
	4	Permanently discontinue	Permanently discontinue
AST, ALT, or Increased Bilirubin	2	Toxicity resolves to Grade 0-1 and the patient has tapered off of corticosteroids.	Toxicity does not resolve within 12 weeks of last dose.
	3-4	Permanently discontinue	Permanently discontinue

Toxicity	Hold Pembrolizumab For NCI CTCAE Grade	Timing for Restarting Treatment	Discontinue Pembrolizumab Permanently
Type 1 diabetes mellitus (if new onset) or Hyperglycemia	T1DM or 3-4	Hold pembrolizumab for new onset Type 1 diabetes mellitus or Grade 3-4 hyperglycemia associated with evidence of beta cell failure.	Resume pembrolizumab when patients are clinically and metabolically stable.
Hypophysitis	2-3	Toxicity resolves to Grade 0-1	Toxicity does not resolve within 12 weeks of last dose or inability to taper corticosteroids to a dose of prednisone 10 mg or less within 12 weeks.
	4	Permanently discontinue	Permanently discontinue
Hyperthyroidism	3	Toxicity resolves to Grade 0-1	Toxicity does not resolve within 12 weeks of last dose or inability to taper off corticosteroids within 12 weeks.
	4	Permanently discontinue	Permanently discontinue
Hypothyroidism	2-4	Therapy with pembrolizumab can be continued while treatment for the thyroid disorder is instituted	Therapy with pembrolizumab can be continued while treatment for the thyroid disorder is instituted.

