 - For **Grade 2 events**, treat with systemic corticosteroids. When symptoms improve to Grade 1 or less, steroid taper should be started and continued over no less than 4 weeks.
 - For **Grade 3-4 events**, immediately treat with intravenous steroids. Administer additional anti-inflammatory measures, as needed.
 - Add prophylactic antibiotics for opportunistic infections in the case of prolonged steroid administration.

- **Diarrhea/Colitis:**

Subjects should be carefully monitored for signs and symptoms of enterocolitis (such as diarrhea, abdominal pain, blood or mucus in stool, with or without fever) and of bowel perforation (such as peritoneal signs and ileus).

- All subjects who experience diarrhea/colitis should be advised to drink liberal quantities of clear fluids (or to administer liberal quantities of clear fluids via PEG tube if present). If sufficient oral or PEG-tube fluid intake is not feasible, fluid and electrolytes should be substituted via IV infusion. For Grade 2 or higher diarrhea, consider GI consultation and endoscopy to confirm or rule out colitis.
- For **Grade 2 diarrhea/colitis** that persists greater than 3 days, administer oral corticosteroids.
- For **Grade 3 or 4 diarrhea/colitis** that persists > 1 week, treat with intravenous steroids followed by high dose oral steroids.
- When symptoms improve to Grade 1 or less, steroid taper should be started and continued over no less than 4 weeks.

- **Type 1 diabetes mellitus (if new onset, including diabetic ketoacidosis [DKA]) or ≥ Grade 3 Hyperglycemia, if associated with ketosis (ketonuria) or metabolic acidosis (DKA):**

- For **T1DM or Grade 3 – 4 Hyperglycemia:**
 - Insulin replacement therapy is recommended for Type I diabetes mellitus and for Grade 3-4 hyperglycemia associated with metabolic acidosis or ketonuria.
 - Evaluate patients with serum glucose and a metabolic panel, urine ketones, glycosylated hemoglobin, and C-peptide.

- **Hypophysitis:**

- For **Grade 2** events, treat with corticosteroids. When symptoms improve to Grade 1 or less, steroid taper should be started and continued over no less than 4 weeks. Replacement of appropriate hormones may be required as the steroid dose is tapered.

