5.7.1 DLT

DLT is defined as the occurrence of a severe adverse event (AE) listed below that is *at least possibly* related to pembrolizumab and occurs within 24 weeks of the initiation of pembrolizumab on either treatment arm. AEs will be graded according to NCI CTCAE version 4.0.

DLT Definition:

Since autoimmune/inflammatory events may occur at any time during the course of treatment, and may occur with evidence of clinical benefit, the following criteria will be used to define DLT:

- Any \geq Grade 4 non-hematologic toxicity **except**:
 - Grade 4 in-field radiation dermatitis for which IMRT is held \leq 1 week (5 fractions).
 - Grade 4 mucositis for which IMRT is held \leq 1 week (5 fractions).
 - Asymptomatic Grade 4 hypomagnesemia or hypokalemia, which corrects to Grade \leq 2 with replacement therapy.
- An alanine or aspartate amino transaminase elevation of greater than three times the upper limit of normal with concurrent elevation of bilirubin two times the upper limit of normal attributable to pembrolizumab should be considered a DLT. Patients meeting this criterion should be permanently discontinued from pembrolizumab.
- Autoimmune toxicity of any grade requiring systemic corticosteroids or other anti-inflammatory that cannot be tapered off in less than 12 weeks.
- Delay in completion of radiation therapy >10 fractions, or inability to complete prescribed IMRT course, due to immune toxicity at least possibly attributed to pembrolizumab.
- Grade ≥ 3 neutropenia with fever (oral temperature $> 39^{\circ}\text{C}$).
- Grade ≥ 3 thrombocytopenia with bleeding.

Patients who experience a DLT will receive no additional doses of pembrolizumab and will be withdrawn from the protocol. Patients may complete cisplatin and radiation per standard of care.

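### Section 5.3.1 sets a later steroid trigger for grade 3 or 4 diarrhea/colitis (more than 1 week) than for grade 2 (more than 3 days)

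*Combined protocol and SAP*

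**What the plan says.** Section 5.3.1 lists supportive care by organ system. It calls the measures suggested, leaves them to what the treating investigator deems necessary, and intends them for events judged related to pembrolizumab. Under Diarrhea/Colitis:

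- A grade 2 event "that persists greater than 3 days, administer oral corticosteroids".
- A grade 3 or 4 event "that persists > 1 week, treat with intravenous steroids followed by high dose oral steroids".
- At grade 2 or higher, with no waiting period, sites are told to "consider GI consultation and endoscopy to confirm or rule out colitis". Fluids are advised for all events.
- Once symptoms improve to grade 1 or less, a "steroid taper should be started and continued over no less than 4 weeks".

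Table 4 covers pembrolizumab only: hold at grade 2-3, discontinue permanently at grade 4. After a grade 2-3 event it may restart when "Toxicity resolves to Grade 0-1 and the patient has successfully tapered off of corticosteroids". The table gives no time for starting steroids.

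**The concern.** A more severe immune-related event would normally be treated at least as early as a milder one. Here the two adjacent bullets run the other way. A site that follows them literally would start steroids later for a related grade 3 or 4 colitis than for a grade 2 one. These bullets are the only colitis steroid timing in the document. The wait also fits poorly with the protocol's own grading in Table 13, where grade 4 means that urgent intervention is indicated and grade 3 means that hospitalization is indicated. The same colitis text asks sites to watch for bowel perforation. What is at stake is the safety guidance given to sites, not an operating characteristic of the trial.

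**Working it through.** The plan gives no figure to reproduce. The check sets the steroid directions of section 5.3.1 side by side and then sizes the gap.

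**Steroid directions in section 5.3.1**

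| Toxicity | Grade 2 | Grade 3-4 |
|---|---|---|
| Diarrhea/colitis | oral, after more than 3 days | IV then high-dose oral, after more than 1 week |
| Pneumonitis | systemic, no wait stated | "immediately treat with intravenous steroids" |
| Hypophysitis | corticosteroids, no wait stated | IV then oral, no wait stated |
| Hyperthyroidism | beta-blocker suggested, no steroid | IV then oral, no wait stated |
| Hepatic | IV or oral, no wait stated | IV, no wait stated |
| Renal | oral, no wait stated | IV, no wait stated |

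Diarrhea/colitis is the only toxicity with a wait at grade 3-4. It is also the only one with a wait at grade 2.

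**Could the grade 2 bullet cover higher grades?** It names grade 2 alone. The bullet on GI consultation just before it is written for grade 2 or higher, so the inclusive form was used where it was meant.

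**Gap with both clocks from onset.** More than 3 days is first met on day 3 + 1 = 4. More than 7 days is first met on day 7 + 1 = 8. The gap is 8 − 4 = 4 days.

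**Gap if the clock starts on reaching the grade.** The text does not say which start is meant. Suppose an event spends d days at grade 2, with d from 0 to 3, and then becomes grade 3. The IV trigger falls on day d + 8. Had the event stayed at grade 2, the oral trigger would have fallen on day 4. The gap is (d + 8) − 4 = d + 4, that is 4, 5, 6 or 7 days for d = 0, 1, 2, 3. If d exceeds 3, oral steroids are already due and only the step to IV is late.

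These are differences between written triggers, not delays seen in patients.

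**Dose cost of earlier steroids.** The minimum taper is 4 × 7 = 28 days. Doses are due every 21 days (± 3), and 28/21 = 1.33, so a taper in mid-course spans 1 or 2 scheduled doses. At intervals of 18 and 24 days the ratios are 1.56 and 1.17, again 1 or 2 doses. A taper that starts after the eighth and last dose spans none. The range is therefore 0 to 2. It counts the minimum taper only; a longer taper, or steroid treatment before the taper, would add to it. Some of these doses would be missed anyway because of the hold. The count does not apply to grade 4, where pembrolizumab is stopped for good.

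**The case against.** The strongest reply is that the effect on practice is limited.

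- The measures are suggested and subject to investigator judgment.
- Section 5.1.5 permits glucocorticoids for an event of clinical interest of suspected immune origin.
- Holding or stopping pembrolizumab, fluids and the GI prompt carry no wait.
- Section 5.3.1 refers to a separate guidance document on events of clinical interest, which sites may have and which could not be checked here.
- Section 5.3.1 also asks that other causes, such as infection, be ruled out, which could justify some wait.

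All of this stands as a limit on the consequence. None of it explains a longer wait at a higher grade. Time to exclude infection would apply at grade 2 as well, and the treatment guidance applies once the event is judged related to pembrolizumab.

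A reader might infer that earlier steroids are forbidden, because section 5.1.5 otherwise prohibits glucocorticoids and the list of events of clinical interest in section 12.4.2 does not name colitis. The documents do not support that. The list is introduced as what such events include, and section 5.3.1 itself directs steroids for colitis.

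A reader might also infer that grade 4 is already dealt with, because a related grade 4 event within 24 weeks is a dose-limiting toxicity (DLT) and, under section 5.7.1, "Patients who experience a DLT will receive no additional doses of pembrolizumab and will be withdrawn from the protocol". That rule stops pembrolizumab. It does not say when the colitis is treated, so it does not confine the problem to grade 3.

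**Conclusion.** The point holds as an error in the written safety guidance. The grade 3 or 4 trigger is later than the grade 2 trigger by 4 days if both clocks run from onset, or by 4 to 7 days if the clock starts on reaching the grade after 0 to 3 days at grade 2. Confidence is high for the wording. It is lower for what sites actually do, because the guidance is discretionary and the separate guidance document was not available.

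Two stronger conclusions are not supported. First, the documents give no basis for estimating patient harm. Second, a reader might infer that a primary metric is affected, since one DLT criterion is "Autoimmune toxicity of any grade requiring systemic corticosteroids or other anti-inflammatory that cannot be tapered off in less than 12 weeks". The documents give neither a direction nor a size for any effect of earlier steroids on that criterion, so it adds no weight. The DLT definition, stopping boundaries, sample size and acceptance rule are not in question on this point.

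**What to change.** In the Diarrhea/Colitis bullets of section 5.3.1, set the grade 3 or 4 steroid trigger no later than the grade 2 trigger, that is at most 3 days. Check the revised text against the guidance document on events of clinical interest. State whether persistence is counted from onset or from reaching the grade.

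Removing the grade 3 or 4 wait altogether is an option by analogy with the other grade 3-4 bullets. The documents do not require it, and the analogy is imperfect because diarrhea/colitis alone also has a wait at grade 2.

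The cost is one phrase and the definition, a protocol modification with prospective IRB approval (section 13.3.1), and a notice to sites. The downside is that some events that would have settled will be given steroids and a taper of at least 4 weeks. After a grade 3 event this can delay restart, because Table 4 requires the patient to be off corticosteroids and missed doses are skipped. About 0 to 2 scheduled doses are at risk. The first dose after chemoradiotherapy may instead be delayed by up to 3 weeks. No statistical section needs to change.
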